10 SAFETY REPORTING

10.1 Adverse Event Reporting

Investigators should give details of all AEs and SAEs from date of first study treatment until 30 days after the last exposure to blinded therapy. SUSARs related to the

Investigational Medicinal Product (IMP) will need to be reported to the sponsor irrespective of how long after IMP administration the reaction occurred.

Patients should be followed up until resolution of the event. All AEs should be recorded on the appropriate page of the CRF, including date of onset, grade, seriousness, duration and relationship to study therapy and outcome.

Collection, recording and notification of AEs (including serious and non serious events and reactions) to the sponsor by the trials office will be done according to the sponsor's SOP and the agreement between both parties.

10.2 Expedited Serious Adverse Event Reporting

Investigators or their designee should report all SAEs in an expedited manner (i.e. within 24 hours of becoming aware of the event) according to the following procedure.

- Complete an SAE Form (If more than one SAE occurs, each event will be recorded separately on a new form) and a fax cover sheet
- The SAE Form can be completed and signed by a member of the site trial team delegated this responsibility by the Investigator, but should be checked and counter signed by the Investigator at a later date
- Fax the SAE Form to the Trials Office. Ensure that a return fax is received back from the Trials Office, confirming receipt
- Adhere to any local institutional policy relating to SAE reporting
- Continue to follow the patient up until clinical recovery is complete or any sequelae has stabilised
- Provide follow-up information on an SAE Form on resolution of the event

NOTE: when assessing SAEs the Investigator must assume that the patient received sorafenib

The Trials office will report to the sponsor all SAEs & SARs in accordance with the sponsor's SOP and the agreement between both parties.

10.3 SAEs that do not require Expedited Reporting

Hospitalisation for the purpose of the TACE treatment, and lasting for up to 7 days after that treatment, does not require reporting unless associated with other serious events. Hospitalisation lasting for >7 days post TACE OR re-admissions within 7 days (i.e. if the patient is discharged from hospital and then returns within 7 days), require reporting in the usual manner as outlined above.

Although not reported as a serious adverse event, details of length of stay in hospital will be captured on the relevant page of the CRF.

10.4 Notification of deaths

All deaths will be reported to trials office irrespective of whether the death is related to disease progression, the Investigational Medicinal Product, or an unrelated event within 24 hours. The Trials Office will notify the sponsor of SAE related deaths within 7 days.

10.6 Codebreaks

Following the closure to recruitment all patients will be notified of their treatment allocation and no further codebreaks will be necessary in the event of a serious adverse event being deemed unexpected and possibly, probably or definitely related to the IMP and classified as a SUSAR by the Investigator or TACE-2 Clinical Co-ordinator.

10.7 Reporting by Sponsor

All unexpected serious adverse reactions will be notified to the sponsor immediately according to the sponsor's SOP. Reporting by the Sponsor or Sponsor's delegated representative is in line with the "Detailed guidance on the collection, verification and presentation of adverse reaction reports arising from clinical trials on medicinal products for human use April 2006".

For the purposes of the trial sorafenib and matching placebo are both classed as Investigational Medicinal Products (IMP), whilst TACE is classed as background treatment and a Non Investigational Medicinal Product (NIMP).

• SUSAR reporting in Member State concerned

The Sponsor, or delegated representative, shall report all individual events which are unexpected and suspected to be related to sorafenib, or matching placebo, or to be linked to an interaction between sorafenib, or matching placebo, and TACE, to the Competent Authority and the Ethics Committee in the Member State concerned as follows:-

If a SUSAR is categorised as a fatal or life threatening SUSAR, a minimal data set of all individual events will be sent within 7 days with detailed follow-up information provided within an additional 8 days.

All other events categorised as SUSARs will be reported within 15 days to the Competent Authority and the Ethics Committee in the concerned Member State.

Regular SUSAR reports to Ethics Committees in other Member states

All SUSARs from other Member States will be periodically reported at least every 6 months as a line listing accompanied by a brief report by the Sponsor/Trials Office highlighting the main points of concern. Those periodic reports shall only include SUSARs reported within the period covered by the report.

Development Safety Update Report (DSUR)

In addition to the above, the sponsor or delegated sponsor's representative shall submit, once a year throughout the clinical trial or on request, a safety report to the Competent Authority and the Ethics Committee of all concerned Member States, taking into account all new available safety information received during the reporting period. The DSUR will

describe concisely all new safety information relevant for this trial and it will assess the safety of subjects included in this study. Details of all SUSARs and any other safety issue which arise during the course of the trial will be compiled into a report, and sent to all Investigators by a TACE-2 trial representative. The frequency of reporting will be dependent on the volume of SUSARs generated and the significance of the safety issue but it will be at least every 6 months. The line listing will present data on all SUSARs, regardless of the medication administered (e.g. active/placebo), thereby when possible and appropriate, the blind is maintained and the risk of inadvertently informing the investigators with regard to the identity of the medication is avoided.

Other Safety Issues Identified During the Course of the Trial

The Trials Office/Sponsor shall notify the Competent Authority and the Ethics Committee in all the concerned Member States immediately if a significant safety issue is identified during the course of the trial.

Bayer/Biocompatibles UK

Safety reporting to Bayer or Biocompatibles by the sponsor or delegated sponsor's representative will be in accordance with the signed agreement between both parties.

11 QUALITY OF LIFE

QoL is an important outcome measure and as such all patients will be invited to participate in the QoL study. Patients who consent will be assessed using validated instruments developed by the EORTC QoL Group: the EORTC QoL questionnaire (QLQ-C30) version 3 and EORTC QLQ-HCC18 a site-specific module for HCC. The EORTC questionnaires will assess both general and hepatocellular specific aspects of quality of life. Patients will also be asked to complete a EuroQoL (EQ-5D) questionnaire which will enable the patient's current health state to be valued for use in calculating quality-adjusted life years (QALYs). These will be collated into a QoL booklet which will be given to patients to complete prior to treatment with the reasons for any non-compliance recorded. QoL booklets will be coordinated with routine clinic visits and requested at baseline, pre TACE, week 10 and 6-weekly thereafter until progression.

The EORTC QLQ-HCC18 site-specific module for HCC has completed phases 1 to 3 of questionnaire development, and has been approved by the EORTC module development committee and currently submitted for publication.

12 DEFINITION OF OUTCOME MEASURES

12.1 Progression Free Survival (PFS)

PFS is defined as the interval between the date of randomisation and the date of progression or death from any cause. Progression will be defined by RECIST criteria (see Appendix 2 for more detail) compared against the baseline pre-randomisation CT or MRI. The imaging modality used to define progression must be the same as that used at baseline. Surviving patients without progression will be censored at date last seen.

12.2 Overall Survival

Overall survival time is the time between the date of randomisation and death from any cause. Patients discontinuing the study, lost to follow-up or still alive at the end of the study will be censored at the last known date alive.

12.3 Time to Progression (TTP)

TTP is defined as the interval between the date of randomisation and the date of progression. Progression will be defined by RECIST criteria compared against the baseline pre-randomisation CT or MRI. The imaging modality used to define progression must be the same as that used at baseline. Patients who have not progressed by the end of the study will be censored at date last seen. Patients who have not progressed and have died will be censored at their date of death.

12.4 Toxicity

Adverse events and serious adverse events will be graded according to the revised NCI Common Terminology Criteria for Adverse Events version 4 (NCI CTCAE v4) from start of study treatment up to 30 days after last administration of study treatment or until end of study.

12.5 Disease Control [CR+PR+SD] and progression [PD]

Response will be assessed using the RECIST guidelines. Response according to modified RECIST criteria will also be recorded separately but only PD by RECIST will trigger unblinding. The scan done prior to randomisation will be considered the baseline scan and the same modality must be used for all follow-up assessments. PD will be externally validated. Unblinding will occur upon local diagnosis of PD confirmed by receipt at the Trials Unit of a Progression Notification Form, signed by the PI. (See also section 3.2)

12.6 Quality of Life (QoL)

QoL will be assessed using the EORTC QoL questionnaire (QLQ-C30) version 3, EORTC QLQ-HCC18, a site-specific module for HCC and the EuroQoL (EQ-5D) questionnaire

requested at baseline, pre TACE, week 10 and 6-weekly thereafter until progression. QoL will be scored according to the EORTC QLQ-C30 manual and guidelines.

13 STATISTICAL CONSIDERATIONS

13.1 Power Calculations

A feasibility questionnaire was sent out to all centres that had expressed interest to obtain an estimate of recruitment. 15 UK sites returned the questionnaires as well as 6 sites from both France and Italy.

As it was estimated that the French and Italian sites would not open until years 2 and 3 respectively, the estimated recruitment was calculated as follows:

	UK	France	Italy	Total estimate
Estimated annual recruitment	218	112	170	
Year 1	50%	0%	0%	109
Year 2	100%	50%	0%	273
Year 3	100%	100%	50%	415
			Total for 3 years / 2	399

The total estimate for recruitment from interested sites was divided by two to provide a cautious estimate of 399 patients over 3 years.

The primary research question to be addressed is to compare efficacy in terms of progression-free survival (PFS) of TACE plus sorafenib and TACE plus placebo in patients with hepatocellular cancer. Current evidence is that TACE has shown a 35% 12-month PFS rate and median PFS of 8.9 months (TACE-1, personal communication). The SHARP trial has shown a 3-month increase in median Time To Progression (TTP) using Sorafenib from 12.3 to 24 weeks (HR=0.69) and improvement in median overall survival from 7.9 to 10.7 months.

Power calculations are based on one-year and median PFS rates and expectant Hazard Ratio (HR). Confirmation of the planned recruitment sites has allowed power calculations to be based on a 36 month accrual period and 12 month follow up period of all patients. The one-year PFS on the TACE plus placebo arm is assumed to range between 30-40% and the proposed trial will be powered to detect a clinically meaningful absolute increase in PFS of 12% with sorafenib. This equates to the detection of 3.5 month increase in median PFS from 8.9-12.4 months and an estimated HR TACE+S of 0.72, translated assuming exponential survival. Calculations assume a log-rank test will be carried out with a two-

tailed 5% significance level. Recruiting 206 patients in each treatment arm over a 36 month period, with additional follow-up of 12-months following the recruitment period, will allow these survival differences to be detected using a 2-sided level of significance of α =0.05 with 85% power. If the true median survival times are 8.9 and 12.4 months for TACE with placebo and sorafenib respectively, the null hypothesis that the survival distributions are equal can be rejected with 85% power. Numbers of patients are estimated using PS software (version 3.0.2) developed by Dupont and Plummer at Vanderbilt University and which is available free from their website. The software is based on methods described by Schoenfeld and Richter in Biometrics 1982.

Machin and Campbell sample size software (version 2.5) calculate that the study will require at least 340 events to achieve 85% power, as above.

The assumptions behind these sample size calculations will be re-examined periodically by an independent data monitoring committee during the course of the trial, and modified as appropriate.

The number of patients lost to follow-up for the primary outcome measure is expected to be minimal (existing studies report \leq 6%) but will obviously be monitored rigorously. The Data Monitoring Committee (DMC) may advise recruitment of additional patients based on the number of patients lost to follow up if numbers are higher than anticipated. The number of patients who do not comply with the protocol is expected to be low. All protocol violators will be reported but will be included in the final analysis within their randomised group on an intention-to-treat basis.

13.2 Analyses of Outcome Measures

All analyses will be carried out on an intention to treat basis, retaining patients in their randomised treatment groups and including protocol violator and ineligible patients, in order to maintain the unbiased comparison of treatments created by the randomisation procedure. A sensitivity analysis excluding ineligible patients may be conducted and reported. Analyses will be according to the detailed Statistical Analysis Plan (SAP) for the Trial using the statistical software packages Stata, SAS and R. The SAP is version controlled and any amendments to the plan will be documented.

The primary aim is to test the null hypothesis of no difference between the two treatment arms in terms of PFS. Disease status is assessed under the RECIST criteria. The primary analysis will consider the local disease assessment only. A sensitivity analysis based on the results of the central review of disease status may be performed. Survival estimates (progression-free, overall and time to progression) will be calculated using the method of Kaplan and Meier, and the Mantel-Haenszel version of the log-rank test will be used to assess differences in survival estimates across treatment groups and across important patient characteristic or histological groups. Any treatment effect will be adjusted by

stratification factors and other identified prognostic factors using stratified log-rank analyses and in a multivariate setting using Cox proportional hazards and/or random effects modelling. Hazard ratios of the treatment effect (without significance testing) within identified prognostic subgroups will be estimated and presented graphically with tests of heterogeneity. Analyses of overall survival may be confounded since patients can crossover to the active arm upon disease progression. These analyses are sensitive to the assumption of proportional hazards and, as such, methods that adjust for this confounding will be considered once the assumption can be assessed.

Toxicity will be graded according to the NCI CTCAE v4 criteria and the proportions of grade 3/4 toxicity will be reported descriptively across treatments. Additional treatment required during or after protocol treatment will be recorded and presented descriptively across treatment groups.

Objective Disease Response will be determined according to the RECIST criteria and patients will be grouped for comparison across treatments according to their 'best' response. Response rates are calculated by dividing the total number of patients with CR or PR (on 'best' response) by the total number of patients randomised per treatment group. The proportions of patients achieving a response will be compared descriptively with 95% CI and compared across treatments using Pearson's chi-square test.

Quality of life will be analysed using longitudinal statistical methods comparing treatment group with appropriate consideration given to missing data due to dropout and death. Questionnaire responses will be combined and transformed into dimension scores and the mean change from baseline score compared using the Mann-Whitney test. Standardised area under the curve analysis will be used to assess mean observed symptomatic and functional QoL over a complete period of 12 months from randomisation whilst minimising multiple testing. Global QoL scores and utility scores form the EQ-5D will be assessed in a quality-adjusted survival analysis to enable simultaneous assessment of QoL and survival, to account for drop-out due to death and censored QoL estimates (from patients remaining alive). Quality adjusted survival analysis within 12 months of randomisation using the integrated quality-survival product method will be used.

The number of additional TACE procedures will be recorded in each arm and reported descriptively with medians and ranges.

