3.3 Blinding and Ongoing Trial Treatment

Patients will be randomised to receive sorafenib or matching placebo in a double-blind fashion such that neither the Investigator, nor the patient will know which combination is being administered. Following the trial's closure to recruitment, all patients will be notified of their treatment allocation. Patients on blinded sorafenib treatment prior to closure, who in consultation with their medical team, may continue to receive further supplies of sorafenib as deemed necessary and where the withdrawal of the treatment would be detrimental to that patients ongoing care. Patients on blinded placebo treatment may remain on trial following the trial's closure to recruitment and receive TACE procedures only. Patients who remain on trial will be re-consented to the trial following the trial's closure to recruitment.

Study medication will be labelled with a unique number (Treatment Pack Number) which will be assigned to a patient.

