APPENDIX 2: RECIST CRITERIA

The following contains excerpts from the RECIST criteria plus trial specific instructions.

For more information regarding RECIST and a full copy of criteria, go to http://www.eortc.be

Ref. E.A. Eisenhauera, P. Therasseb, J. Bogaertsc *et al.* New response evaluation criteria in solid tumours: Revised RECIST guideline (version 1.1). 45, 228-247 (2009).

NOTE All imaging will be independently reviewed by IXICO to confirm response or progression

1. Measurability of Tumour Lesions at Baseline

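### All patients are unblinded when recruitment closes, yet primary PFS rests on local assessment alone and the central-review analysis is optional; up to about 18–25% of expected events fall after that point

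*Protocol*

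**What the plan says.** The title and section 3.1 describe a double-blind, placebo-controlled trial. Section 3.3 ends the blind for everyone at closure to recruitment: "all patients will be notified of their treatment allocation". Section 10.6 repeats this. Under 3.3, patients may stay on trial after re-consent, either continuing sorafenib after discussion with their medical team or, on placebo, having TACE alone. The treating team therefore knows the allocation too.

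PFS follow-up continues past that point. Section 13.1 plans "additional follow-up of 12-months following the recruitment period". Section 13.5 sets the final analysis at least 12 months after the last blinded treatment visit, and section 16 keeps the study open for a year after the last recruitment. Section 12.1 counts progression or death and censors event-free patients when last seen, with no cut at unblinding.

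On who reads the scans, section 13.2 says "The primary analysis will consider the local disease assessment only", followed by "A sensitivity analysis based on the results of the central review of disease status may be performed". Appendix 2 says "All imaging will be independently reviewed by IXICO to confirm response or progression", and section 12.5 provides for external validation of progression.

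**The concern.** Local reading is a defensible basis for the primary endpoint while the reader does not know the treatment. Section 3.3 removes that protection for the last year of follow-up, and 13.2 was not adapted to it. Once allocation is known, it can influence whether a borderline scan is called progression and, after week 22, when the scan is done. Sections 7.2 and 8.7 and Appendix 12 leave scans after week 22 to local standard of care, whereas Appendix 2 (2.2.1) says 3-monthly.

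The direction cannot be predicted. An investigator might hold back a progression call for a patient on sorafenib, or call one sooner for a patient on placebo so that sorafenib can be offered. Expectations could also run the other way. The independent reads that could show such a bias are arranged, but the protocol does not commit to using them in any PFS analysis.

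**Working it through.** **Inputs (section 13.1).** "Recruiting 206 patients in each treatment arm over a 36 month period"; 12 months' further follow-up; "If the true median survival times are 8.9 and 12.4 months for TACE with placebo and sorafenib respectively"; exponential survival, HR 0.72; "using a 2-sided level of significance of α =0.05 with 85% power"; at least 340 events.

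**Reproducing the plan's figure.** Freedman's formula: events = ((1+HR)/(1−HR))² × (1.960+1.036)² = (1.72/0.28)² × 8.98 = 339. This matches 340. Schoenfeld's formula gives 333.

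**Expected events.** With hazard λ = ln 2/median, uniform accrual over A months and F months of further follow-up,

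P(event) = 1 − [exp(−λF) − exp(−λ(A+F))]/(λA).

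Here λ = 0.0779 per month (placebo) and 0.0559 (sorafenib), with 206 per arm.

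| Accrual | Events by closure (F=0) | Events at F=12 | After closure |
|---|---|---|---|
| 36 months (13.1) | 137.0 + 117.3 = 254.3 | 178.9 + 160.7 = 339.5 | 85.3 (25.1%) |
| 48 months (about 4 years, 3.4) | 286.7 | 354.3 | 67.6 (19.1%) |
| 51.5 months (November 2010 to mid first quarter 2015, 3.4) | 294.0 | 357.7 | 64 (18%) |

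The first row also reproduces the 340. On that row, about 69 placebo and 89 sorafenib patients would be event-free when told their allocation. If accrual over 36 months is instead weighted by the yearly totals in the 13.1 feasibility table (109:273:415), the share rises to 33.9%. Loss to follow-up at 6% per year, with uniform accrual, gives 24.3%.

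**Removing deaths.** A death is a PFS event but nobody reads it. The protocol gives no share of deaths without prior progression. Assuming 10–30% of late events are such deaths:
- 25.1% × 0.9 to 0.7 = 23% to 18%
- 18% × 0.9 to 0.7 = 16% to 13%

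Locally read, open-label progressions are therefore about 13–23% of all events under uniform accrual.

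**Power if PFS were cut at closure.** About 254 events remain. Schoenfeld: Φ(√(254/4) × |ln 0.72| − 1.96) = Φ(2.62 − 1.96) = 0.745. Freedman gives 0.738, and Schoenfeld with HR 8.9/12.4 gives 0.753. Power falls from the planned 85% to about 74–75%.

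**What misreading could do: illustration only.** I simulated log-rank tests with no true effect, median PFS 10.5 months and scans every 12 weeks. The one-sided error favouring sorafenib should be 2.5%.

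| Assumed reading after closure | 36 months' accrual, no deaths | 51.5 months' accrual, 20% deaths |
|---|---|---|
| Half of sorafenib progressions called one scan late | about 6–7% | about 4–5% |
| All sorafenib progressions called one scan late | about 12–13% | about 7–8% |
| Half called late in both arms | no inflation | no inflation |

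Nothing in the protocol supports any particular misreading rate. If the delay fell on placebo instead, the bias would run against sorafenib.

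**The case against.** - **The statistical analysis plan may deal with this.** Section 13.2 defers detail to that plan, which is not shown, and extra sensitivity analyses are normal content for it. This stands in part: a reader might infer that no analysis anywhere would reveal the bias, and the protocol alone cannot show that. But 13.2 itself fixes local reading for the primary analysis and describes the central-review analysis as optional, for a period that 3.3 makes open-label. The analysis plan could not change the primary reading without contradicting the protocol.
- **The size is easily overstated.** A reader might infer that a quarter of the primary events are read open-label. The documents do not support that. The 25% belongs to the 36-month timeline, includes deaths, and assumes every event-free patient re-consents and stays. Section 3.4's longer timeline gives 18–19%.
- **A false-positive risk of 13% might be quoted.** That is a worst case with every late sorafenib progression delayed, no placebo shift and no deaths.
- **Most readings remain blinded.** Some 75–82% of expected events come before closure. Unblinding at an individual's progression (12.5) follows the local call, so it does not bias that call. Both statements are correct, and the problem is confined to the closure unblinding.
- **Late events could take their dates from central review inside the primary analysis.** This is tempting but unsound. Re-dating only locally called progressions misses those an unblinded investigator has not called, needs a rule for unconfirmed progression, and changes the endpoint definition at a calendar date.

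**Conclusion.** The point holds and should be fixed, though it does not invalidate the primary analysis. The protocol combines a closure unblinding of all patients, about a year of further PFS follow-up and a local-only primary reading, with no commitment to use the independent review it has arranged.

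On exponential PFS with medians of 8.9 and 12.4 months, 206 per arm and uniform accrual over 36 to 51.5 months, 18–25% of expected PFS events occur after unblinding. That is a ceiling for open-label readings under those accrual assumptions; with an assumed 10–30% of late events being deaths, it is about 13–23%. Late-weighted accrual would raise both figures, and patients leaving after closure would lower them. The protocol establishes the exposure to bias. It establishes neither its direction nor its amount.

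**What to change.** In section 13.2:

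1. For PFS by independent review, change 'may' to 'will'. State that readers are blind to allocation and read all scans, including those not locally called progression, and that the result is reported alongside the local analysis.
2. Add a pre-specified sensitivity analysis that censors PFS at the date of the closure unblinding. It also removes any effect of known allocation on scan timing, which central reading cannot correct. With about 254 events and 74–75% power on the design assumptions, it should not be the primary analysis.
3. State that the local-assessment primary analysis is open-label after closure and that its conclusion must be read with items 1 and 2.

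The analysis plan should match. The cost is wording, a little more analysis work and waiting for the central read to finish. Sample size and follow-up do not change.
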